1 BACKGROUND

1.1 Minimally Invasive Esophagectomy for Esophageal Carcinoma

Esophageal carcinoma is the 7th most common cause of death from cancer in men in the United States (U.S.). An estimated 16,910 new cases will be diagnosed in the U.S. in 2016, resulting in 15,690 deaths (2). Multimodality treatment for esophageal carcinoma includes chemotherapy, radiation, and surgery in the form of esophagectomy. During an esophagectomy, a majority of the esophagus is resected, and the stomach is narrowed to form a tube, creating a “gastric conduit” that is then relocated from the abdominal cavity into the thoracic cavity. Because both vagus nerves are resected with the specimen, it is theorized that patients may develop gastric dysmotility and pylorospasm, with resulting delayed gastric emptying or gastric outlet obstruction. These are both major complications, as they may lead to aspiration and pneumonia, inability to tolerate oral intake and maintain adequate nutrition, and the need for additional procedures.

One of the major controversial issues currently is how to prevent delayed gastric emptying. Several methods have been implemented to improve gastric emptying during open esophagectomy, with inconclusive results. In the minimally invasive setting, surgeons are utilizing intra-pyloric botulinum toxin injection to prevent pyloric spasm and thus minimize gastric outlet obstruction. Retrospective studies comparing botulinum toxin to historical controls demonstrate inconclusive results regarding the ability of botulinum toxin to decrease rates of delayed gastric emptying. This study aims to test whether it is necessary to use botulinum toxin as a pyloric drainage procedure during minimally invasive esophagectomy. We hypothesize that it is not effective in preventing delayed gastric emptying, and that performing botulinum injection adds cost and time to an already lengthy procedure, without decreasing the procedure complication rate or benefitting patient outcomes.

Improving gastric emptying is crucial to not only maintaining independent nutrition, but also in preventing devastating pulmonary complications including aspiration and subsequent pneumonia. In the era of open esophagectomy, several types of drainage procedures were employed during esophagectomy in an attempt to prevent gastric outlet obstruction. These include pyloroplasty (full-thickness longitudinal incision closed transversely), pyloromyotomy (incision through muscle only, preserving integrity of mucosal layer), and finger fracture (manual pressure on the pylorus, causing muscle disruption). Other surgeons elected not to perform any type of drainage procedure. Advocates of the “no drainage” procedure believed that surgical manipulation of the pylorus during drainage procedures leads to short-term inflammation and edema, which may *cause* gastric outlet obstruction despite that this procedure is designed to prevent such occurrence. In addition, pyloric drainage procedures may lead to dumping syndrome, bile reflux, or leak at the pyloroplasty site, leading to intra-abdominal or intra-thoracic sepsis and even death (3). Possible long-term side effects include scar or stricture formation. Alternatively, no drainage procedure may cause gastric outlet obstruction, leading to inability to tolerate oral diet, aspiration, and pneumonia. Whether or not to perform a pyloric drainage procedure is controversial.

With newer minimally invasive esophagectomy techniques, many surgeons omitted drainage procedures, as they are technically challenging to perform minimally invasively. Other surgeons use botulinum injection at the pylorus as a minimally invasive pyloric drainage procedure, with

the theory this relaxes the muscle without causing inflammation, edema, or risk of leak. Intraoperative botulism toxin injection is safe and simple to perform, without significantly adding to the total operative time. It does however add significant cost to the procedure, approximately \$1,000 per treatment (1). Botulinum toxin injection into the pyloric sphincter has a pharmacologic duration of three to five months (4).

There is much controversy as to the optimal surgical management of the pylorus. A recent review of studies performed on this topic in the past ten years concluded that pyloric drainage procedures were associated with a non-significant trend towards delayed gastric emptying and biliary reflux, while not affecting the incidence of dumping (5). Two other meta-analyses supported pyloric drainage, showing decreased rates of gastric outlet obstruction and improved gastric emptying (6, 7). These meta-analyses reviewed randomized controlled trials published between 1984-2002, prior to minimally invasive technique and botulinum use. Over the past ten years significant changes were made to the way esophagectomies are performed, and these studies do not apply to our patient population today. Major changes in technique include the transition to minimally invasive technique, stapled technique for anastomosis and tissue transection, and tubularization of the stomach conduit as opposed to use of the whole stomach. With minimally invasive techniques, surgical pyloric drainage procedures are difficult to perform, and frequently omitted. When the whole stomach is used as a conduit, the conduit becomes redundant, and such a large reservoir is conducive to gastric stasis. With a narrower conduit, surgeons advocate drainage procedure is unnecessary because the occurrence of redundancy and stasis is lower. Lastly, these studies were published prior to the use of botulinum toxin.

Three retrospective reviews comparing botulinum to pyloric drainage procedures versus no drainage procedure during open esophagectomy have found a significant benefit of botulinum in preventing gastric outlet obstruction, with varying effect on rate of aspiration events and other comorbidities (1, 3, 8). However, a fourth retrospective review of patients undergoing open esophagectomy, patients receiving botulinum injection experienced *higher* rates of gastric outlet obstruction, requiring additional procedures for pyloric dilation compared to patients undergoing pyloromyotomy or pyloroplasty (9). Although these studies were performed using the open esophagectomy technique, they highlight the issues with the data we currently base our practice on. These studies have all been underpowered or flawed, are retrospective in nature, and lack objective criteria in determining requirement for secondary intervention. We are unable to determine if botulinum toxin as a pyloric drainage procedure is a necessary step in an already complex operation. Standardized reporting of postoperative gastric outlet obstruction with delayed gastric emptying and thresholds for intervention are necessary to determine if botulinum toxin as a pyloric drainage procedure is a necessary step in an already complex operation. No prospective randomized study has been published, or to the author's knowledge is in process, to assess the use of intra-pyloric botulinum toxin in the minimally invasive setting as a pyloric drainage procedure.

1.2 Risks and/or Benefits

Risks:

By omitting the pyloric botulinum toxin injection, there is a risk of delayed gastric emptying causing nausea, vomiting, aspiration, pneumonia, prolonged nasogastric decompression, inability

to tolerate oral diet and lengthening hospital stay. Delayed gastric emptying is a known complication after esophagectomy, and a common complication. This complication occurs even with botulinum injection in about 30% of patients (7). One published study concluded that patients receiving botulinum toxin injection experienced higher rates of delayed gastric emptying (9). In most cases of delayed gastric emptying, symptoms may be treated with medications and if severe, by endoscopic procedures, such as botulinum toxin injection or balloon dilation. Therefore, if a patient who did not receive pyloric botulinum toxin injection develops gastric outlet obstruction, he may undergo an endoscopic procedure to alleviate his symptoms. Rarely, severe delayed gastric emptying with complete obstruction may require a return to the operating room.

The drug used in this study is OnabotulinumtoxinA (botulinum toxin type A, Botox[©]). When injected intramuscularly, botulinum toxin inhibits the release of acetylcholine from nerve endings at neuromuscular junctions in the local muscle (10). Without release of acetylcholine, neurotransmission between peripheral nerve endings and muscle fibers cannot occur, and the muscle becomes weak or paralyzed (10). Botulinum toxin is used for cosmetic procedures, and is also FDA-approved to treat cervical dystonia, strabismus, and primary axillary hyperhidrosis (11). Off-label uses of botulinum toxin in the gastrointestinal tract include achalasia and refractory anal fissure, in addition to pyloric injection during esophagectomy.

Benefits:

We hypothesize that pyloric botulinum toxin injection does not prevent delayed gastric emptying and is an unnecessary portion of the minimally invasive esophagectomy. If it is found that botulinum toxin injection does not lead to lower rates of delayed gastric emptying, then this procedure may be omitted, saving cost and side effects associated with the medication, and potential side effects of employing a pyloric drainage procedure, including pyloric edema, dumping syndrome and bile reflux. Pyloric edema from receiving botulinum toxin injection may actually cause delayed gastric emptying. The current rates of pyloric edema, dumping syndrome, and bile reflux are unclear at this time, and will be directly assessed in this study during the nuclear medicine emptying study.

2 RATIONALE

This study will help clarify if a pyloric drainage procedure is necessary in patients undergoing minimally invasive esophagectomy. Over the past ten years significant changes were made to esophagectomy technique including transition to minimally invasive technique, stapled technique for anastomosis and tissue transection and tubularization of the stomach conduit as opposed to use of whole stomach. With a narrower conduit, a drainage procedure may be unnecessary since the occurrence of redundancy and stasis is lower.

3 OBJECTIVES

3.1 Primary Objective

- Determine if intra-pyloric botulinum toxin injection (Botox[©]) during a minimally invasive esophagectomy decreases postoperative occurrence of delayed gastric emptying.

3.2 Secondary Objectives

[figure not shown]
- Determine if intra-pyloric botulinum toxin injection during a minimally invasive esophagectomy:
 - Reduces the number of repeat procedures for delayed gastric emptying within 90 days,
 - Decreases time to oral intake meeting 100% of nutritional requirements,
 - Reduces the incidence of pulmonary complications directly related to delayed gastric emptying,
 - Reduces hospital length of stay related to delayed gastric emptying and,
 - Increases patient quality of life

4 METHODOLOGY

4.1 Study Design

This is a double arm, single-blinded randomized trial evaluating the use of botulinum toxin injection as a pyloric drainage procedure. The study is expected to accrue patients over 4 years. The study schema is depicted below in **Figure 1**.

Figure 1 Study Schema

All patients considered for minimally invasive esophagectomy in our surgery practice will receive routine work-up and multidisciplinary evaluation and care for esophageal carcinoma, which may include neoadjuvant therapy. Patients will be given a patient consent form that will inform them of the possible risks and benefits of this study. Patients will undergo the standard of care preoperative work-up, during which it will be determined if they meet the inclusion and exclusion criteria summarized in **Section 5.1** and **Section 5.2** prior to enrollment in the study. If criteria are met, patients will be randomized by the study coordinator, per methods determined by the statistician. The randomization allocation will be shared with the surgical team from the study coordinator to the surgeon prior to the surgery and discussed during the surgical time-out. The next 50 patients who meet the study criteria will be randomized to either the intrapyloric botulinum injection arm or the non-botulinum treatment arm. All participants will sign a surgical consent prior to minimally invasive esophagectomy.

All patients will undergo routine minimally invasive esophagectomy. If randomized to the botulinum arm, patients will undergo the standard minimally invasive esophagectomy performed at RPCI, including intra-pyloric botulinum injection. If randomized to the no botulinum arm, patients will undergo the standard minimally invasive esophagectomy performed at RPCI **excluding** the pyloric drainage procedure with botulinum injection. The patient and radiologist

will be blinded to the treatment arm. The surgeon, due to the nature of the intervention, will not be blinded to the treatment arm.

The standard of care for minimally invasive esophagectomy at RPCI is outlined in the following postoperative pathway. **All patients follow this pathway unless clinical status dictates otherwise:**

- Patients leave the operating room with a nasogastric tube (NGT) tip at or beneath the esophago-gastric anastomosis, and a feeding jejunal-tube (j-tube).
- Unless prohibited by medical condition, tube feeds are started through the j-tube at 20 mL/hour. Tube feeds are advanced to goal after return of bowel function.
- The NGT is removed.
- If there is no concern for aspiration-such as hoarseness, altered mental status, or limited mobility, and the patient is alert and able to protect the airway, oral diet is started with sips of clear liquids.
- Diet is advanced to full liquids. The nutritional goal, which continues at hospital discharge, is for the oral full liquid diet to meet 50% of calculated caloric needs, and the remaining 50% given as supplemental tube feeds through the j-tube. Patients remain on a full liquid diet for two weeks postoperatively.
- A gastrografin swallow study or CT esophagram is performed to evaluate for any signs of anastomotic leak.
 - This study may also be used to assess gastric emptying. A single radiologist will evaluate the gastrografin study/CT esophagram (1):
 - Quantifying gastric emptying by gastrografin swallow or CT esophagram will allow comparison of our results to previous nonrandomized studies (1).
- Patients are discharged from the hospital if they are medically stable and tolerating 100% of nutritional needs as a combination of orally or through j-tube. Any clinical signs of delayed gastric emptying causing regurgitation, vomiting or aspiration will delay hospital discharge until the risk of aspiration is low.
- The day that the first nutritional goal is met will be recorded, when 50% nutritional needs are met with oral full liquid intake and 50% supplemental tube feeds.
- Hospital length of stay attributed to delayed gastric emptying: If patients have intractable nausea and vomiting, or experience a pulmonary event related to aspiration, this will be recorded as attributed to delayed gastric emptying. Prolonged hospital length of stay will be defined as hospital admission past Postoperative Day #14 attributed to delayed gastric emptying.
- If it is uncertain whether a pulmonary event is related to delayed gastric emptying, a formal swallow evaluation will be performed by a speech language pathologist.

- Patients will receive non-opiate and opiate pain relief medications in the postoperative period. Opiate pain medications should only be administered if adequate pain control is not met with non-opiate pain medications.

As a participant in this study the patient will undergo a ***nuclear medicine emptying study*** to assess for conduit function. This study will be obtained within the window of Postoperative Visit #2 (± 14 days). *Prior to the nuclear medicine emptying study*, the patient must be fasting for at least 6 hours; including oral intake and any supplemental j-tube feeds. The fasting glucose should be measured and less than 275 mg/dL. Patients should be off all narcotic pain medications for the 48 hours prior to the nuclear medicine emptying study.

- 120 mL of liquid egg white product (Egg Beaters) will be radiolabeled with 1 mCi of Tc99m, cooked and then scrambled. The patient will be instructed to ingest the meal within 10 minutes. Images will be obtained every 15 minutes for up to four hours. If the patient vomits part of the meal at any time during the test, it will be recorded on the study report.
- During the study, for the time between the images, the patients may be sitting, standing, or walking, but should remain in close proximity to the nuclear medicine facility. Patients will be monitored for any symptoms of delayed gastric emptying during this time. Participants will answer a questionnaire to assess for gastrointestinal symptoms during the nuclear medicine study (See **Appendix C**).

A single nuclear radiologist, who is blinded to the randomization group, will assess gastric emptying on the nuclear emptying study. There is no standardized method for reporting conduit emptying by this method. Two published studies on this topic have used time to 50% gastric emptying as an endpoint (8), and categorized 50% gastric emptying into ranges, with >180 minutes categorized as “delayed,” within 180 minutes as “intermediate,” and immediate emptying as “rapid” (12). We will measure time to 50% gastric emptying in all patients, and categorize similar to the above description, as follows:

Table 1 50% Gastric Emptying Times and Definitions:

Definition	50% Emptying Time
Rapid	Immediate emptying, no radiotracer seen on first image obtained at 15 minutes
Intermediate	$<$ or $=$ 150 minutes
Delayed	$>$ 150 minutes

This time modification is based on the current guidelines and normal limits for gastric retention assessed by nuclear scanning (13). The report will also include the percentage of tracer retained the following times after meal ingestion: 1, 2, 3, and 4 hours.

To ensure the radiologist interpreting the nuclear medicine and gastrografin studies/CT esophagram remains blinded, the radiologist should not open the “operative note” documents in

the electronic medical record. During study interpretation, if the radiologist requires clarification regarding the operative procedure, he should contact the operating surgeons directly. The randomization group will not be listed in any other part of the electronic medical record.

Primary Endpoint

- Postoperative delayed gastric emptying assessed radiographically as “severe” by nuclear medicine emptying study compared to “intermediate,” and “rapid” emptying. “Severe” delayed gastric emptying will be defined as scoring of “delayed” on nuclear emptying study. Patients assessed as “intermediate” or “rapid” on nuclear medicine emptying study will be considered to have normal conduit function.

Secondary Endpoints

- Postoperative delayed gastric emptying assessed radiographically by gastrografin swallow /CT esophagram.
- Postoperative delayed gastric emptying assessed clinically by the following:
 1. Quality of life score assessed by EORTC QLQ-C30 OES18.
 2. Pulmonary events directly related to delayed gastric emptying, as assessed by the operating surgeon. Pulmonary events include pneumonia, acute aspiration, and respiratory failure requiring intubation.
 3. Gastrointestinal and nutritional status: Requirement of NGT past Postoperative Day #7, or need to reinsert NGT, witnessed nausea, vomiting, or regurgitation directly related to delayed gastric emptying. This does not include postoperative ileus. Tolerance of full liquid diet at hospital discharge and meeting nutritional goals of time to resumption of 50% caloric needs orally by Postoperative Day #7, 75% caloric needs orally by Postoperative Day #21, and 100% caloric needs orally by Postoperative Day #35.
 - “Moderate” delayed gastric emptying will be defined as clinical symptoms requiring medical therapy.
 - “Severe” delayed gastric emptying will be defined as clinical symptoms requiring secondary procedure.
 4. Hospital length of stay attributed to delayed gastric emptying.
 5. Number of secondary procedures within 90 days due to delayed gastric emptying. Secondary procedures include endoscopic or operative procedures for delayed gastric emptying.
 - Requirement of secondary procedure will be graded as “Severe” delayed gastric emptying

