6.6 Outpatient Postoperative Follow-Up Visits

Study participants will be followed for data collection for 90 days (routine post-esophagectomy follow-up and surveillance, per standard of care). The following evaluations will be performed during the outpatient postoperative course, unless otherwise clinically indicated:

- In the postoperative period, patients return to office for outpatient follow-up approximately one to three weeks after discharge (“Postoperative Visit #1”). This visit is standard of care and can be scheduled per PI discretion. Physical exam and vital signs will be conducted at this visit. The dietician will assess oral intake, and supplemental tube feeds adjusted accordingly. Day until patient tolerates 75% and 100% of nutritional needs orally will be recorded as per nutritionist assessment.
- As a participant in this study, patients in both randomization groups will undergo a nuclear medicine emptying study. The nuclear medicine emptying study may occur within the window of Postoperative Visit #2 (\pm 14 days) to assess dynamic conduit function. This test can be extended beyond post-operative Visit #2 at PI’s discretion. Patients will be monitored for any symptoms of delayed gastric emptying during this time by questionnaire (See **Appendix C**), to determine if nuclear medicine study findings correlate with concurrent clinical symptoms.
 - Prior to the nuclear medicine emptying study, the patient must be fasting for at least 6 hours, including oral intake and any supplemental j-tube feeds. If the patient is a diabetic, the glucose level should be measured and less than 275 mg/dL within 2 hours of the study. Opiates must be held for 48 hours prior to the study. Patients should not be on any of the medications listed in **Appendix B** within the 48 hours prior to the study. Patients will remain in the nuclear medicine suite during this time, and will be required to sit upright, and may walk around the room. During the study, for the time between the images, the patients may be sitting, standing, or walking, but should remain in close proximity to the nuclear medicine facility.
- Post-surgical symptom evaluation based on clinical factors during the outpatient follow-up visits, and additionally by phone conversation between outpatient follow-up appointments if clinically indicated.

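### Does section 9.4 need a planned analysis of the half-emptying time, hourly retention and the scan-symptom link?

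*Combined protocol and SAP*

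**What the plan says.** Section 4.1 describes the scan. "Images will be obtained every 15 minutes for up to four hours", and T50 is taken from it: "We will measure time to 50% gastric emptying in all patients, and categorize similar to the above description". Table 1 gives three categories: rapid (no tracer on the 15-minute image), intermediate (T50 up to 150 minutes) and delayed (T50 above 150 minutes). Retention is recorded too: "The report will also include the percentage of tracer retained the following times after meal ingestion: 1, 2, 3, and 4 hours".

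The same section acknowledges that "There is no standardized method for reporting conduit emptying by this method" and describes earlier work as having put "50% gastric emptying into ranges, with >180 minutes categorized as" delayed. The primary endpoint is delayed against the other two categories. Patients scored intermediate or rapid "on nuclear medicine emptying study will be considered to have normal conduit function". T50, retention and the three-level category are not listed as secondary endpoints.

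Section 6.6 gives the Appendix C questionnaire a purpose: "to determine if nuclear medicine study findings correlate with concurrent clinical symptoms".

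Section 9.4 treats the scan as a dichotomous outcome, tested by a one-sided stratified CMH test. Its list of secondary outcomes contains no nuclear-scan measure. A general sentence after that list promises descriptive and graphical summaries of all variables by arm.

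**The concern.** Three things are recorded or aimed at without a named analysis.

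- **By-arm description.** T50, hourly retention and the rapid count have no named table. The general sentence in 9.4 stands under the secondary analysis, after a list that omits them.
- **The four-hour limit.** A patient not half-emptied at 240 minutes has no observed T50, and nothing says how it is recorded. These are the slowest patients, and there would be more of them in the arm with more delay. An analyst who dropped them would understate the difference between arms.
- **Scan and symptoms.** Section 6.6 states an aim that 9.4 does not take up.

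At stake is what the trial can report beyond one percentage. The earlier work used T50 and a 180-minute cut, whereas this trial cuts at 150. A delayed rate at 150 minutes cannot be set directly beside a rate at 180. Section 4.1 plans a comparison with earlier studies for the swallow study but not for the scan that carries the primary endpoint.

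**Working it through.** **1. The plan's own figures.** Section 9.1 states 85.0% power at delayed rates of 0.30 and 0.70 with n=50 and an interim at 30. A two-stage simulation of the one-sided CMH test with the stated rules gives 84.5% (eight equal strata) to 86.1% (eight unequal strata, assumed prevalences). One-sided O'Brien-Fleming-type spending at information 30/50 = 0.6 gives 0.011396 at the interim, as stated, and 0.046528 at the end against 0.046533. Nothing in the concern alters these inputs.

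**2. Is the primary endpoint affected by the four-hour limit?** No. Images come every 15 minutes, and 150/15 = 10, so the cut-off falls on the tenth image. An unreached T50 exceeds 240, hence exceeds 150, and the patient is delayed.

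**3. How many T50 values are unobserved?** The documents give no T50 distribution. Assume T50 is log-normal with log-SD s and P(T50 > 150) = p. Then

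P(T50 > 240) = 1 − Φ(ln(240/150)/s − z_p), with ln 1.6 = 0.470, z_0.70 = 0.524 and z_0.30 = −0.524.

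The upper quartile is 150·exp(s(z_p + 0.674)) and the median is 150·exp(s·z_p).

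| s | p = 0.70: above 240 | median | upper quartile | p = 0.30: above 240 | upper quartile |
|---|---|---|---|---|---|
| 0.3 | 15% | 176 | 215 | 2% | 157 |
| 0.5 | 34% | 195 | 273 | 7% | 162 |
| 0.7 | 44% | 217 | 347 | 12% | 167 |
| 1.0 | 52% | 253 | 497 | 16% | 174 |

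With 25 patients per arm this is about 4 to 13 at a 70% rate and 0.5 to 4 at a 30% rate. The upper quartile at 70% passes 240 only when s exceeds 0.470/1.199 = 0.39. The median does so only when s exceeds 0.470/0.524 = 0.90.

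**4. Does the handling matter?** Take s = 0.5 at 70% against 30%. The true medians are 195 and 115 minutes, a difference of 80. Dropping values above 240 gives 157 and 110, a difference of about 46. Keeping them as above 240 leaves both medians exact. The poor choice is plainly poor, and the sensible one needs no modelling.

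**5. Can the missing quantities be recovered?** Yes. If retention falls steadily, more than 50% retained at hour 3 means T50 above 180, and more than 50% at hour 4 means T50 above 240. Both retentions are recorded, so a count at the earlier studies' cut can be made whatever 9.4 says. Under the same model with s of 0.5 to 0.7, rates of 70% and 30% at 150 minutes become 56–60% and 19–22% at 180.

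**6. Would a formal T50 test add anything?** The table compares simulated power of a two-sided stratified rank test (van Elteren) on T50, with values above 240 tied as worst, against the planned two-stage CMH test. It assumes stratified blocks of 4, stratum prevalences of 80%, 50% and 20%, and s of 0.5 to 0.7. In this setup the CMH test has 88% power at 70/30.

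| Control / Botox delayed | Rank test | CMH |
|---|---|---|
| 70/30, whole curve shifts | 88–89% | 88% |
| 50/30, whole curve shifts | 38% | 40–41% |
| 30/10, whole curve shifts | 64% | 53–54% |
| 70/30, only crossing 150 | 62% | 88% |
| 30/10, only crossing 150 | 21% | 53–54% |

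The rank test gains in one scenario, is about level in two and loses clearly in two.

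**7. The symptom table.** As an example, a symptom in 15 of 25 delayed and 8 of 25 other patients is a difference of 28 points, with a Newcombe 95% interval of about 0.5 to 50. A cross-tabulation is all these numbers support, and the scan category and questionnaire answers it needs are already collected.

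**The case for a change.** The best case for a change is that it is nearly free: a few lines in 9.4 on data already collected, with the primary test untouched. Without them someone chooses after seeing the data whether to drop, extrapolate or cap the late T50 values, and step 4 shows that dropping them would nearly halve the difference in medians. The general sentence in 9.4 does not settle that choice, nor does it say how to relate the scan to symptoms.

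The omissions stand as described. Their weight is limited for four reasons.

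- Section 4.1 measures T50 in order to categorise, and 9.4 analyses the category. T50 and retention were never declared endpoints.
- The general sentence in 9.4 can fairly be read to cover by-arm description of what is recorded, although that is not its only reading.
- No stated rule yields a wrong result. Showing unreached values as above 240 minutes is routine practice.
- The comparison with earlier work is stated as an aim only for the swallow study, and the documents do not show what T50 summaries the earlier scan studies report.

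A formal T50 test would bring its own problems. It would need cautions for both kinds of early stop, because estimates after a superiority or an inferiority stop are biased, and 9.1 puts inferiority stops at 42.1% when there is no effect. Its null result would also be easy to over-read: with no effect, the 95% interval for the probability that a Botox patient empties faster typically runs from 0.34 to 0.66 at n=50.

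**Conclusion.** No change to the plan follows. Section 9.4 is silent on three descriptive matters, and analysts can fill each from recorded data: counts of the three categories and hourly retention by arm; T50 median and quartiles with unreached values shown as above 240 minutes; and one table of scan category against the Appendix C symptoms. The primary endpoint, CMH test, boundaries, n=50 and stated 85.0% power are unaffected, because 150 minutes lies inside the 240-minute window.

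The share of unobserved T50 values is an assumption-dependent range, not an estimate: about 15% to 52% of controls at a 70% delayed rate (log-SD 0.3 to 1.0), and about 7% to 12% at a 30% rate (log-SD 0.5 to 0.7). The lower rate is worth keeping in view, since 9.4 says the institution's own rate is below the literature figures, though on a stricter criterion. A formal test on T50 is a matter of preference and is not required.
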